^d Intracranial hemorrhage with or without associated edema is not considered a neurotoxicity feature and is excluded from ICANS grading. It may be graded according to CTCAE v5.0 (Lee, 2019).

It has been speculated that high levels of IL-6 may directly mediate neurotoxicity in this situation (Lee [A], 2014). A human anti-IL-6 monoclonal antibody, tocilizumab, may reverse this

neurotoxicity, but it would not be expected to cross the blood brain barrier, and efficacy in this setting has not been confirmed. Therefore, it is suggested that corticosteroids be the primary therapy in this situation, and tocilizumab considered only if this proves ineffective.

Clinical management of neurotoxicity:

- Monitor subjects closely for signs and symptoms of these events (including the use of mental status and neurologic examinations).
- If neurotoxicity becomes evident, draw an unscheduled blood sample for cytokine analysis at that time, and again 4 hours later, unless scheduled cytokine monitoring is already in progress on the same visit day.
- If neurologic toxicity is Grade 4, discontinue plamotamab.
- For Grade 3 neurologic toxicity, withhold drug until the toxicity has recovered to \leq Grade 1 (mild) and has remained at \leq Grade 1 for at least 3 days before restarting therapy. Restart at 75% of the previous dose. Escalate back to full dose at the time of the next dose if \geq Grade 2 toxicity does not recur. If \geq Grade 2 toxicity reoccurs at 75% dose, or if $<$ Grade 2 toxicity takes more than 7 days to resolve, discontinue permanently. If Grade 3 neurologic toxicity persists for more than 7 days, permanently discontinue plamotamab.
- For severe neurologic symptoms, administer additional dexamethasone 10 mg intravenously and repeat every 12 hours if symptoms do not abate rapidly.
- For recurrent seizures, anticonvulsant therapy may be necessary.

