4.7. Dose Modification Guidelines

Treat subjects experiencing a significant toxicity with standard medical interventions (eg, use of filgrastim to treat neutropenia, acetaminophen for fever) as appropriate. For infusion reactions/CRS and neurotoxicity management, Investigators may use their standard treatment practices, and for additional guidance, see [Section 4.6](#).

In general, if a > Grade 2 toxicity prevents dosing > 14 days and/or if 2 consecutive doses are missed (this applies to weekly and Q2W dosing), the subject may require discontinuation from the plamotamab or tafasitamab treatment. Subjects may reinitiate study drug, even after 2 or more missed consecutive doses of plamotamab or tafasitamab, if the Investigator determines that the benefit outweighs the risk and the toxicity (if applicable) can be controlled by concomitant medication or other means. Medical Monitor approval is required for delays of > 14 days and/or 2 consecutive doses.

During weekly dosing of plamotamab and/or tafasitamab, if a subject's dose is held for ≥ 7 days, it should be considered missed. During Q2W dosing of plamotamab and/or tafasitamab, if a subject's dose is held for ≥ 14 days, it should be considered missed. If a subject's dose is given out of window or delayed for safety concerns, including AEs, it is not considered a protocol deviation.

Plamotamab may be resumed after prolonged dose delay for more than one cycle for reasons other than toxicity (eg, comorbidity, pseudoprogression, or delayed response). Resuming initial treatment course may be allowed on a case-by-case basis if the Investigator and the Sponsor consider this in the best interest of the subject. As a safety measure, the dose may be lowered to the priming dose for re-titration. Study assessments, including local and/or central labs, are to be collected per the Schedule of Assessments.

For toxicities that could overlap (eg, CRS, infusion reaction, hematologic toxicities), detailed dose modifications by grade are presented in [Table 8](#) below:

Table 8: Dose Modifications for Select Toxicities

Adverse Reaction	Severity	Dosage Modification

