	
Neutrophil count of 1,000/μL or less for at least 7 days OR
 
Neutrophil count of 1,000/μL or less with an increase of body temperature to 100.4°F (38°C) or higher OR
 
Neutrophil count less than 500/μL
	
 • Withhold plamotamab, tafasitamab, and lenalidomide and monitor CBC weekly until neutrophil count is 1,000/μL or higher. • Resume plamotamab and tafasitamab at the same dose and lenalidomide at a reduced dose. Refer to lenalidomide prescribing information for dosage modifications. • If recurrence, repeat drug withholding (first bullet above) and lenalidomide reduction steps until minimal lenalidomide dose is reached per lenalidomide prescribing information. • If recurrence at 5 mg lenalidomide, repeat drug withholding steps then reduce the next scheduled plamotamab dose to 75% of the previous dose.
Febrile Neutropenia	Grade 3 (severe) & Grade 4 (life-threatening)	
 • Withhold plamotamab, tafasitamab, and lenalidomide and monitor CBC until neutrophil count is Grade \leq 1. • Once subject is afebrile, off antibiotics and neutrophil count is Grade \leq 1, resume all therapy at the same dose and schedule.
Neurotoxicity	Grade 3 (severe)	
 • Withhold plamotamab and manage signs and symptoms (see Section 4.6.1.7) until the toxicity has recovered to \leq Grade 1 (mild) and has remained at \leq Grade 1 for at least 3 days before restarting therapy. • Reduce next scheduled plamotamab dose to 75% of the previous dose. If \geq Grade 2 toxicity does not recur, escalate plamotamab to full dose in subsequent administrations. • If \geq Grade 2 toxicity recurs at 75% dose, or if $<$ Grade 2 toxicity takes more than 7 days to resolve, permanently discontinue plamotamab. • Tafasitamab and lenalidomide dosing is not modified.
	Grade 4 (life-threatening)	
 • Stop infusion immediately, if still infusing and permanently discontinue plamotamab.
AST, ALT, bilirubin, and alkaline phosphatase in the absence of CRS	Grade 3 (severe)	
 • Withhold plamotamab and manage signs and symptoms until the toxicity has recovered to \leq Grade 1 (mild) or baseline. • If a Grade 3 liver toxicity persists $>$ 14 days and/or 2 consecutive doses are missed and the toxicity cannot be attributed to another cause, permanently discontinue plamotamab. • Tafasitamab and lenalidomide dosing is not modified.

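### Section 4.6.1.7 requires permanent discontinuation of plamotamab when Grade 3 neurotoxicity lasts more than 7 days; the matching row of Table 8 omits that stop

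*Protocol*

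**What the plan says.** Three places in the protocol bear on plamotamab after Grade 3 neurotoxicity.

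- **Section 4.6.1.7 (Neurotoxicity).** The drug is withheld until the event has come down to Grade 1 or lower and stayed there for at least 3 days. Then: "Restart at 75% of the previous dose". Full dose follows if Grade 2 or higher does not recur. Plamotamab stops for good if Grade 2 or higher recurs at the 75% dose, or if toxicity below that level is slow to clear (below "Grade 2 toxicity takes more than 7 days to resolve, discontinue permanently"). The rule ends with a separate sentence on persistence: "If Grade 3 neurologic toxicity persists for more than 7 days, permanently discontinue plamotamab".
- **Section 4.7, Table 8, Neurotoxicity, Grade 3.** The row begins: "Withhold plamotamab and manage signs and symptoms (see Section 4.6.1.7) until the toxicity has recovered to" Grade 1 or lower, again for at least 3 days. It continues: "Reduce next scheduled plamotamab dose to 75% of the previous dose". Re-escalation and the stop on recurrence follow as in Section 4.6.1.7, as does the slow-resolution clause (below "Grade 2 toxicity takes more than 7 days to resolve, permanently discontinue plamotamab"). There is no sentence on Grade 3 that persists.
- **Section 4.7, general text.** If toxicity above Grade 2 prevents dosing for more than 14 days, and/or 2 consecutive doses are missed, the subject may require discontinuation. Reinitiation is allowed on the investigator's benefit-risk judgement, and "Medical Monitor approval is required for delays of > 14 days and/or 2 consecutive doses".

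**The concern.** A permanent stop for a serious toxicity of this drug class appears in the narrative section but not in the table that Section 4.7 introduces as the detailed dose modifications by grade. A site working from the table would re-dose a subject whom the narrative section removes from plamotamab.

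The first stake is subject safety. Section 4.6 says the three-drug combination had not been tested in humans, and the benefit-risk case in Section 2.4.4 leans on dose modifications for specific toxicities.

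The second is interpretation of the safety data. Section 11.8 lists treatment-emergent AEs leading to permanent discontinuation of plamotamab as an AE-related endpoint, Section 4.2.2 makes neurological AEs a secondary endpoint, and Section 4.1.1 uses Part 1 safety to choose the Part 2 dose. If sites apply different stopping rules, discontinuation and exposure partly reflect which page was followed.

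**Working it through.** No sample size, power or error-rate figure is involved, so the check is a comparison of the texts followed by one worked case.

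**Step 1: the two Grade 3 rules side by side.**

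| Element | Section 4.6.1.7 | Table 8 row |
|---|---|---|
| Withhold until Grade 1 or lower, held at least 3 days | Yes | Yes |
| Restart at 75% of previous dose | Yes | Yes |
| Return to full dose if Grade 2 or higher does not recur | Yes | Yes |
| Permanent stop if Grade 2 or higher recurs at 75% | Yes | Yes |
| Permanent stop if toxicity below Grade 2 takes more than 7 days to resolve | Yes | Yes |
| Permanent stop if Grade 3 persists more than 7 days | **Yes** | **Absent** |

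Five elements match and one is missing from the table. The only 7-day limit in the Table 8 row concerns toxicity below Grade 2.

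**Step 2: a worked case.** Assume Grade 3 neurotoxicity starts on a plamotamab dosing day (call it Day 1) and lasts 8 days (Days 1 to 8). It then falls to Grade 1 or lower, stays there for 3 days (Days 9 to 11), and resolves within 7 days of the fall, so the slow-resolution clause is not met on any reading.

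- Section 4.6.1.7: 8 days is more than 7, so plamotamab is permanently discontinued.
- Table 8 as written: the recovery condition is met, so the next scheduled dose from Day 12 onward is given at 75%.

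**Step 3: does the general rule in Section 4.7 close the gap?** Its trigger is dosing prevented for more than 14 days and/or 2 consecutive missed doses.

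- Dosing every 2 weeks: the next dose is due on Day 1 + 14 = Day 15, after recovery. No dose is missed.
- Weekly dosing: doses fall due on Days 8 and 15. Only the Day 8 dose falls before Day 12, so at most 1 dose is missed. Even if nothing is given until Day 15, that dose is 15 − 8 = 7 days late.

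Neither schedule reaches the trigger, so Medical Monitor approval is not called for. Where the trigger is reached, the consequence is discretionary, whereas the Section 4.6.1.7 sentence is mandatory.

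**Step 4: does any text rank the two sources?** None was found. The Table 8 pointer to Section 4.6.1.7 is attached to managing signs and symptoms. For neurotoxicity management, Section 4.7 lets investigators use their standard practices and refers to Section 4.6 for additional guidance. For CRS, Section 4.6.1.6 sends the reader to Section 4.7 and Table 8 for rechallenge, which supports treating the table as the dosing reference.

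**Step 5: is silence in the table informative?** Other Table 8 rows do carry duration limits: Grade 3 liver toxicity (more than 14 days and/or 2 consecutive missed doses), Grade 4 liver toxicity (more than 3 days), and Grade 2 CRS recurring after a Grade 3 or 4 event (more than 10 days to reach Grade 1 or lower). A reader could fairly take the absence of one for persistent Grade 3 neurotoxicity to mean that none applies.

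**The case against.** The best reply is that this is an omission, not a pair of opposed instructions. Table 8 never says that Grade 3 neurotoxicity beyond 7 days may be re-dosed. A site can obey both texts by applying the Section 4.6.1.7 stop to long events and the 75% restart to the rest, and the row does name Section 4.6.1.7. Re-dosing under Table 8 alone also still requires recovery, a reduced dose and a permanent stop on recurrence at Grade 2 or higher. It stands that the two texts can be read together and that the table gives no express permission. It does not stand that the cross-reference settles the matter, because the pointer covers symptom management and the row otherwise reads as a complete rule.

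A reader might also infer several stronger points that the documents do not support:

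- *That the time limits run against severity*, because toxicity below Grade 2 has a 7-day limit and Grade 2 has none. In both places the clause follows the 75% restart and shares a sentence with recurrence at that dose, so it reads naturally as covering toxicity after restart. There, Grade 2 or higher stops plamotamab at once and lower grades only after 7 days. The wording could be clearer, but the text and table agree on it.
- *That the conflict covers events of 8 to 14 days.* Table 8 sets no upper limit. The 14 days in Section 4.7 count time that dosing is prevented, not the duration of Grade 3.
- *That Section 4.6.1.7 stops where Table 8 restarts.* Both restart at 75% after shorter events.

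**Conclusion.** The point holds as an internal inconsistency. For Grade 3 neurotoxicity that persists more than 7 days and then recovers to Grade 1 or lower for at least 3 days, Section 4.6.1.7 requires permanent discontinuation of plamotamab, while Table 8 followed as written leads to a 75% dose. The general rule in Section 4.7 has a different trigger and a discretionary consequence, so it does not resolve the difference.

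The discrepancy is one missing sentence, and it affects only Grade 3 events longer than 7 days. The conclusion assumes that a site uses Table 8 as its dosing instruction and does not carry over the stop from Section 4.6.1.7. The worked case also assumes that residual toxicity clears within 7 days and that the event starts on a dosing day.

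The practical effect on this trial is now small: SAP Sections 1, 4.1 and 7 report early termination with 3 subjects enrolled and listings only. A reader might infer that reported discontinuations were distorted, but nothing in the documents shows that such an event occurred. The point matters for the protocol as written and for any reuse of its text.

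**What to change.** Reconcile Section 4.6.1.7 with the Grade 3 neurotoxicity row of Table 8 so that both state the same single consequence for Grade 3 neurotoxicity that persists. State whether the general delay rule in Section 4.7 applies to neurotoxicity or gives way to the specific rule, and say which source governs if text and table differ. The sponsor's clinicians must decide which rule stands; this review takes no position on it. The change is to protocol wording only and leaves the design, sample size and analysis untouched. With the study closed, it is worth making wherever these sections are carried into another protocol.

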4.6.2. Allergic/Hypersensitivity/Infusion-related Reactions

Infusion-related reactions have been reported for tafasitamab as well as plamotamab. An allergic reaction is often caused by a type 1 hypersensitivity mechanism due to immunoglobulin E (IgE)-mediated release of histamines and prostaglandins, although a direct interaction with mast cells and basophils can also occur. However, infusion-related reactions, including serious and fatal reactions, are not uncommon with monoclonal antibody therapeutics and tend to occur most frequently during the first few infusions.

Signs and symptoms usually develop during or shortly after drug infusion in hypersensitivity reactions, are more likely to occur after several doses of the drug and are largely related to histamine release. Typical signs and symptoms include rash/urticaria, flushing, pruritus, fever, dyspnea, cough, and hypotension, although the following may also occur ([Lenz, 2007](#)):

- Arthralgia
- Bronchospasm
- Confusion/mental status changes/delirium
- Dizziness
- Fatigue (asthenia, lethargy, malaise)
- Hallucinations
- Headache

- Hypertension
- Myalgia
- Nausea/vomiting
- Rigors/chills
- Diaphoresis
- Tachycardia

Allergic/hypersensitivity/infusion-related reactions are managed according to institutional practices and guidelines. Allergic/hypersensitivity reactions will be defined according to the NCI-CTCAE, Version 5.0 (NCI-CTCAE, 2017) definition of allergic reaction.

4.6.2.1. Safety Run-in and Part 2, Arm A (Plamotamab, Tafasitamab and Lenalidomide)

Infusion-related reactions have been observed with plamotamab and tafasitamab. To mitigate overlapping toxicity with plamotamab, on a given treatment day, tafasitamab must be given first with a minimum of 2 hours between the end of the tafasitamab infusion and the start of the plamotamab infusion. If a > Grade 1 infusion reaction occurs with tafasitamab, delay the plamotamab until the resolution all symptoms of the reaction. Depending on the timing of the resolution of all symptoms, it may be necessary to administer the plamotamab the following day.

4.6.2.2. Part 2, Arm B (Tafasitamab and Lenalidomide)

Infusion-related reactions have been observed with tafasitamab and lenalidomide. Follow toxicity management instructions provided in the prescribing information for tafasitamab. Refer to [Section 4.7](#) for dosage modifications.

4.6.3. Hematologic Toxicities

Hematologic toxicities, specifically decreases in absolute neutrophil count (ANC) and platelet count, have been observed in clinical trials of tafasitamab and lenalidomide. Decreases in platelets and ANC have also been observed with plamotamab (see [Table 7](#)).

Table 7: Adverse Events of Neutropenia and Thrombocytopenia with Tafasitamab/Lenalidomide and Plamotamab (All Grades)

	Tafasitamab ^a /Lenalidomide	Plamotamab ^b
Neutropenia	51%	20.8%
Thrombocytopenia	31%	24.0%

^a Monjuvi[®] PI, 2021; Minjuvi[®] SmPC, 2021

^b Plamotamab Investigator's Brochure, 2021

These decreases may worsen in grade or duration when the products are given in combination. Monitor blood counts carefully and follow institutional guidelines for the treatment of neutropenia and thrombocytopenia. Treatment may include the use of growth factors and the administration of whole blood/blood product transfusions. Management may also include the delay in the administration of study drugs until the counts return to at least Grade 2 levels. See [Section 4.7](#) for any dose modifications to study drugs.

4.6.3.1. Safety Run-in and Part 2, Arm A (Plamotamab, Tafasitamab and Lenalidomide)

Hematologic toxicities, specifically, decreases in ANC and platelet counts have been observed in clinical trials of tafasitamab and lenalidomide. Decreases in platelets and ANCs have also been observed with plamotamab. These decreases may worsen in grade or duration when the products are given in combination. Monitor blood counts carefully and follow institutional guidelines for the treatment of neutropenia and thrombocytopenia, which may include growth factors and whole blood/blood product transfusions. Management may also include the delay in the administration of study drugs until the counts return to at least Grade 2 levels. See [Section 4.7](#) for any dose modifications to study drugs.

4.6.3.2. Part 2, Arm B (Tafasitamab and Lenalidomide)

Hematologic toxicities have been observed with tafasitamab and lenalidomide. Follow toxicity management instructions provided in the prescribing information for tafasitamab. See [Section 4.7](#) for any dose modifications to study drugs.

4.6.4. Tumor Lysis Syndrome

Tumor lysis syndrome (TLS) is a rare but serious and life-threatening condition arising from rapid release of tumor cellular contents after lysis; resulting metabolic imbalances can lead to acute kidney failure and/or other life-threatening conditions. Subjects with high tumor burden, highly proliferative disease, and/or certain preexisting conditions such as renal disease are at increased risk of TLS.

4.6.4.1. Safety Run-in and Part 2, Arm A (Plamotamab, Tafasitamab and Lenalidomide)

It is unknown whether treatment with plamotamab, tafasitamab, and lenalidomide can cause TLS in R/R DLBCL. The Phase 1 plamotamab monotherapy study in CD20-expressing hematologic malignancies had investigator-reported, any-grade TLS in 4 of 96 subjects (4.2%), of which only 2 of the 80 R/R NHL subjects (2.5%) experienced TLS; importantly, no serious or fatal events of TLS have been reported with plamotamab monotherapy in R/R DLBCL (Plamotamab IB 2021). Likewise, no events of TLS were reported in the Phase 2 open-label, single-arm, tafasitamab plus lenalidomide study in R/R DLBCL (L-MIND) ([Duell, 2021](#)). However, fatal instances of TLS have been reported with lenalidomide in other indications and combinations ([Revlimid[®] PI, 2021](#); [Revlimid[®] SmPC, 2022](#)). All subjects should be assessed for risk of TLS according to institutional practices based on laboratory parameters and tumor bulk prior to initiation of the study medications.

4.6.4.2. Prophylaxis, Monitoring, and Treatment of Tumor Lysis Syndrome

Prophylaxis should be instituted prior to the start of treatment for subjects at high risk for TLS per investigator's assessment. Hospitalization may be considered for subjects considered high risk for TLS per investigator and/or creatinine clearance of < 80 mL/min. Allopurinol (or other xanthine oxidase inhibitors) should be initiated at least 48 hours prior to C1D1 in subjects considered medium to high risk for TLS. Rasburicase is indicated for elevated uric acid levels and monitoring of TLS. During study treatment, all subjects require appropriate laboratory testing prior to administration of study medications including uric acid, potassium, phosphorus, calcium, and

creatinine. Laboratory results should be evaluated in real time. If subjects are not able to consume adequate oral fluids, IV fluids should be added.

If a subject experiences laboratory changes or symptoms suggestive of TLS, treatment with plamotamab, tafasitamab and lenalidomide should be interrupted. Investigators should follow institutional guidelines for treatment of TLS. Study treatment is held until resolution of TLS. If moderate or high risk for TLS remains after resolution, consideration of additional prophylactic measures and/or continued dose interruption or reduction of plamotamab, tafasitamab, or lenalidomide may be considered.

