4.5.2. Part 2: Open-Label Randomized

During Part 2, a total of 200 subjects will be randomized as follows: with a 1:1 ratio of plamotamab and tafasitamab plus lenalidomide versus tafasitamab plus lenalidomide, stratified by IPI risk score at baseline (3 – 5 versus 0 – 2); number of lines of prior therapy (1 versus ≥ 2); and primary refractory (yes versus no). A maximum of 36 primary refractory subjects may be enrolled. Subjects will be randomized only if they have signed the informed consent and are determined to be eligible. The initiation of study treatment will occur within 72 hours of randomization. Study treatment will begin on Study Day -8 with the tafasitamab priming doses.

No blinding is specified given the potential for overlapping toxicities. In the presence of overlapping toxicities, a blinded study may result in dose modifications or reductions of placebo. This may confound the management of toxicities without addressing the source of the toxicity through dose modification or reduction schemes. Therefore, to ensure the safety of subjects, the study will not be blinded.

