7.2. Concomitant Medications

All medications (including over-the-counter-medications and herbals) and blood products that are administered 21 days prior to start of treatment (Day –8) and throughout subject's participation in the study until the 90-day post-treatment follow-up visit must be recorded in the source document and on the eCRF, including date, time, and dose of administration. Concomitant medications for other medical conditions are permitted as clinically indicated, subject to specific requirements outlined below.

Subjects may not concurrently receive:

- Other experimental therapeutics for their malignancy
- Live viral vaccine within 30 days of Day –8, during treatment, within 60 days of the last dose of plamotamab, or within 90 days of the last dose of tafasitamab

Subjects may receive the following concurrent therapy:

- Antiemetics, antidiarrheals, anticholinergics, antispasmodics, antipyretics, antihistamines, analgesics, antibiotics, and other medications intended to treat symptoms
- Prophylactic filgrastim may **NOT** be administered after the first dose but may be administered during subsequent dosing in subjects who experience Grade 3 or 4 neutropenia as per the American Society of Clinical Oncology guidelines ([Robinson, 2018](#)). If a subject develops neutropenia after the first dose, they may be treated with filgrastim after the second or subsequent dose.
- Subjects who experience CRS should receive aggressive intervention and supportive measures. These may include, but are not limited to, acetaminophen, antihistamines, corticosteroids, IV fluids, bronchodilators, epinephrine, vasopressors, oxygen, and tocilizumab (see [Section 4.6](#) for guidance on management).
- Transfusions such as red blood cells (RBCs) and platelets are permitted if medically indicated. These should be leukocyte-filtered and irradiated to prevent development of transfusion-associated, graft-versus-host disease. All attempts should be made to avoid blood product transfusions on the same day as study drug administration.
- Subjects who experience indigestion, nausea, and/or vomiting may be treated with histamine receptor, type 2 antagonists, or proton pump inhibitors
- Subjects may take vitamins and/or supplements provided they are documented on the medication eCRF
- Subjects may have received hepatitis B reactivation prophylaxis with entecavir, tenofovir, or lamivudine

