7.5.2. Day –8, Day –4, and Day –1

- Abbreviated PE (Day –8 and Day –1 only)
- Neurologic examination will be assessed using the ASTCT ICANS Consensus Grading for Adults (Day –1 only, see [Section 4.6.1.7](#))

- Vital signs (supine or sitting position, including heart rate, blood pressure, temperature, respiratory rate, and blood oxygen saturation by continuous pulse oximetry)
- Weight (Day –8 and Day –1)
- ECOG performance status (see [Appendix A](#))
- CBC with differential (percent and absolute) and platelet count (see [Section 7.5.1](#)) (Day –8 and Day –1 only)
- Chemistry panel (see [Section 7.5.1](#)) (Day –8 and Day –1 only)
- Fibrinogen (Day –1 only)
- Coagulation panel (PT/ INR and APTT) (Day –1 only)
- Urinalysis (see [Section 7.5.1](#)) (Day –8 and Day –1 only)
- Urine or serum β -hCG pregnancy test for women of childbearing potential (Day –8 and Day -1 only)
- The following to be sent to the central laboratory per the laboratory manual:
 - Serum sample for rituximab level (Day –1 only)
 - Serum samples for tafasitamab PK and ADA (Day –8 only)
 - Peripheral blood for TBNK, leukocyte flow cytometry (Day –8 only)
 - Peripheral blood for RNA analysis (Day –8 only, prior to tafasitamab dose)
- Administration of tafasitamab on Day –8 and Day –4
- Record concomitant medications and AEs

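### The Day −4 tafasitamab infusion has no scheduled chemistry although Section 4.6.4.2 asks for tumor-lysis labs before study medication, and that section times prophylaxis from two different start points

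*Protocol*

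**What the plan says.** **Laboratory rule.** Protocol Section 4.6.4.2: "During study treatment, all subjects require appropriate laboratory testing prior to administration of study medications including uric acid, potassium, phosphorus, calcium". The sentence ends by adding creatinine, and the next one asks that results be evaluated in real time. Section 4.6.4.3 applies the same guidance to Arm B.

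**Start of treatment.** Section 4.5.2: "Study treatment will begin on Study Day -8 with the tafasitamab priming doses". Section 7.2 dates its medication-recording window from "21 days prior to start of treatment (Day –8". Section 7.5.1 likewise identifies Day −8 with the first dose of study drug.

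**Run-in schedule.** Section 7.5.2 gives tafasitamab on Day −8 and Day −4, but lists: "Chemistry panel (see [Section 7.5.1](#)) (Day –8 and Day –1 only". Table 9 agrees, and its chemistry row is blank at Day −4.

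**Prophylaxis timing.** Two sentences in the same paragraph of Section 4.6.4.2:
- "Prophylaxis should be instituted prior to the start of treatment for subjects at high risk for TLS per investigator's assessment"
- "Allopurinol (or other xanthine oxidase inhibitors) should be initiated at least 48 hours prior to C1D1 in subjects considered medium to high risk for TLS"

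**The concern.** Section 4.6.4.2 is the protocol's TLS safeguard, and it also tells sites to interrupt all three drugs if laboratory changes suggest TLS. That instruction depends on having a result. At the Day −4 infusion the schedule supplies no new one. Footnote j of Table 9 places dosing-day chemistry before any study drug, so the most recent scheduled result at Day −4 predates all treatment and cannot show an effect of the first dose.

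The prophylaxis wording raises a related question. The run-in puts two tafasitamab infusions before C1D1, so starting prophylaxis before treatment and starting it 48 hours before C1D1 are different deadlines. A site must work out for itself which applies to which subject.

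At stake is whether sites apply the safeguard in the same way during the run-in, which every subject in Part 1 and in both arms of Part 2 goes through.

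**Working it through.** No power, alpha or sample size is involved. The check is a comparison of sections and a count of days.

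**Inputs**
- Infusion days: Table 9; Sections 7.1.2 and 7.5.2.
- Chemistry days: Table 9; Section 7.5.2.
- Panel content: Section 7.5.1 (includes uric acid, potassium, phosphorus, calcium and creatinine, so the ordinary chemistry panel would satisfy the rule).
- Day numbering: Section 7.6.1 makes Day −1 the day before C1D1, so there is no Day 0.

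**Step 1. Infusion visits with chemistry, Day −8 to the end of Cycle 2**

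| Infusion day | Chemistry in Table 9 |
|---|---|
| −8 | yes |
| −4 | **no** |
| C1 D1, D8, D15, D22 | yes (4) |
| C2 D1, D8, D15, D22 | yes (4) |

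Infusion days: 1 + 1 + 4 + 4 = 10. With chemistry: 1 + 0 + 4 + 4 = 9. From Cycle 3 on, every infusion day in Table 9 has a panel, so Day −4 is the only gap.

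**Step 2. Age of the nearest scheduled results**
- Day −8 to Day −4: 8 − 4 = 4 days before the infusion.
- Day −4 to Day −1: 4 − 1 = 3 days after it.
- Interval between the two panels: 4 + 3 = 7 days.

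For comparison, Section 7.6.1 lets safety labs precede the visit day by up to 24 hours. That allowance is written for treatment cycles, so it supports the reading that a 4-day-old result is not meant to serve, but does not settle it.

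**Step 3. Latest start that still meets the allopurinol sentence**
- With no Day 0, Day −8 is 8 days before C1D1.
- 48 hours before C1D1 is Day −2.
- Time since the first tafasitamab dose: 8 − 2 = 6 days.
- Time since the second: 4 − 2 = 2 days.

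**Step 4. The two prophylaxis sentences by risk group**

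| Group | Before start of treatment (Day −8) | At least 48 h before C1D1 (Day −2 at latest) |
|---|---|---|
| High risk | stated | stated, for allopurinol |
| Medium risk | not stated | stated, for allopurinol (the only timing given) |

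For high-risk subjects, a start before Day −8 meets both sentences. For medium-risk subjects only the C1D1-based minimum exists.

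**The case against.** **Days −8 to −1 are labelled pretreatment.** Table 9 and the Section 7.5 title use that word, so a rule that applies during study treatment might begin at C1D1. This does not stand. Sections 4.5.2 and 7.2 say in terms that treatment starts on Day −8, and tafasitamab is one of the three named study drugs.

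**The laboratory rule cannot mean every administration.** It says neither \"each dose\" nor how recent the sample must be, and lenalidomide is taken daily on Days 1 to 21 without daily chemistry. This is right, and it defeats a literal per-dose reading. It does not explain why one infusion visit alone lacks a panel that all the others have.

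**A site can comply with everything.** A reader might infer that the sections cannot both be followed. They can: nothing forbids an extra draw on Day −4, and the 48 hours is a minimum, so earlier prophylaxis is allowed. What stands is that the schedule does not ask for the draw, and the allopurinol sentence does not ask for the earlier start.

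**The clinical team may have meant C1D1.** A reader might infer that C1D1 is the wrong anchor. The documents do not show that. Section 4.6.4.1 places risk assessment before study medication begins, and the high-risk sentence uses the start of treatment; only the allopurinol sentence uses C1D1. That is a difference to be explained, not proof of a clinical error.

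**The risk looks small.** Section 4.6.4.1 reports no TLS in the earlier tafasitamab plus lenalidomide study. Its 4 of 96 (4.2%) figure is for plamotamab monotherapy, with 2 of 80 (2.5%) in non-Hodgkin lymphoma, and no plamotamab is given in the run-in. Nor is the 97% fall in peripheral B cells in Section 2.4.3 evidence of tumor lysis; it is offered there in support of mitigating cytokine release. This objection limits the size of the point but does not remove the mismatch.

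**Conclusion.** A narrow inconsistency holds, in two parts:

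1. Following Section 7.5.2 and Table 9 as written omits, at the Day −4 infusion, the chemistry that Section 4.6.4.2 calls for before study medication. This is 1 of the 10 infusion visits through Cycle 2 and the only such visit in the whole schedule.
2. Section 4.6.4.2 uses two start points for prophylaxis without saying how they relate. The later one can be met 6 days after the first tafasitamab dose, and it is the only timing given for medium-risk subjects.

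The first part assumes that the rule covers infusion visits from Day −8, as the stated start of treatment implies.

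The point does not extend to the blood count. It too is missing on Day −4, and a reader might add it, but Section 4.6.4.2 does not list it, so its absence contradicts nothing there.

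The clinical consequence cannot be sized, because the documents give no TLS rate for the tafasitamab run-in. By plan the gap would have applied to about 240 subjects. The SAP (Sections 1 and 4.1) reports early termination with 3 enrolled, and the protocol was in any case to be revised before Part 2. The practical effect is therefore small, and the point matters mainly if this text is reused.

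**What to change.** - Reconcile Section 4.6.4.2 with Section 7.5.2 and Table 9. Either schedule the chemistry panel at the Day −4 visit in both places, or state in Section 4.6.4.2 that Day −4 is an exception.
- In Section 4.6.4.2, say for each prophylaxis sentence which start point it uses (the first dose of any study drug on Day −8, or C1D1) and which risk groups it covers.

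Both choices belong to the clinical team; the statistical review asks only that the sections agree.

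The cost is one cell in Table 9, one edit in Section 7.5.2 and a sentence or two in Section 4.6.4.2. If the panel is added, the visit already exists for an infusion, so the extra burden is one blood sample and the wait for its result. Stating an exception adds no procedure.
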